#### Serious Adverse Events

- Hospitalization of caregiver
- Institutionalization of caregiver
- Emergency room visit of caregiver
- Death of caregiver

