### **Aim 1: I-HoME Protocol and Intervention Development**

**Synchronous Live Video – Patient Symptoms.** The patient symptom component of I-HoME will consist of weekly standardized assessment and management of signs/symptoms (e.g., pain, dyspnea, nausea, vomiting, agitation) experienced by the home hospice patient. In addition, visits on an as-needed basis (based on participant feedback and budget) can be requested by the patient, CG, and/or nurse interventionist, which may focus on a particular symptom or need. Development of the I-HoME protocol will focus on effectively evaluating and treating these symptoms along with other EoL symptoms through standardized assessments and management that incorporate education, non-pharmacologic and pharmacological therapies, and optimal use of hospice resources (e.g., respite, inpatient hospice care, etc.). A prototype intervention and manual of operations will be developed to incorporate existing best care practices and evidence-based research.

Doxy.me is a platform that will be used to conduct synchronous live video interactions between hospice nurses and patients/caregivers. Doxy.me is a secure and HIPAA compliant service. A business associate agreement will be obtained with Doxy.me prior to starting the study.

**Synchronous Live Video – CG Burden.** The CG component of I-HoME will focus on a weekly, standardized assessment and management of burden experienced by the CG. In addition, visits on an as-needed basis (based on participant feedback and budget) can be requested by the CG and/or nurse interventionist, which may address a particular type of burden. Development of the I-HoME protocol will focus on effectively evaluating CG burden and addressing it through education, skill building, coping strategy development, and optimal use of hospice resources (e.g., social work/spiritual care visit, respite, inpatient hospice care, etc.). A prototype intervention and manual of operations will be developed to incorporate existing best care practices and evidence-based research. Doxy.me is a platform that will be used to conduct synchronous live video interactions between hospice nurses and patients/caregivers. Doxy.me is a secure and HIPAA compliant service. A business associate agreement will be obtained with Doxy.me prior to starting the project/intervention.

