We will pilot patient participants (n=20) to answer a survey about their symptoms at baseline, 2 weeks, 4 weeks, and 6-weeks. The survey is the Edmonton Symptoms Assessment Scale (ESAS) which takes approximately 5 minutes to complete. We will also clarify to the patients that the ESAS data collected will not be shared with the clinical team and is for research purposes only. Enrollment of patients will help us understand the feasibility of interviewing hospice patients, and we will also analyze the differences in the ESAS scores from the dyad of caregiver and patient. Participants will be compensated a total of \$50 for their participation. The gift card will be mailed after they have given oral consent and completed the baseline survey questions over the phone. We are suggesting an alteration of written consent and the use of oral consent. The patients are in hospice care and will likely find in-person visits or other forms of written or electronic consents to be burdensome. Their participation involves no more than minimal risks to the subjects, and the oral consent

obtained over the phone will not adversely affect the rights and welfare of subjects. Whenever appropriate, subjects will be provided with additional pertinent information after participation.

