For Aims 2 and 3, all study participants will be interacting with a research assistant while those in the intervention group will also be interacting with a nurse interventionist delivering the I-HoME intervention. Human subject involvement will include data collected from home hospice patients, CGs, and providers by a research assistant. Data will be gathered via: (1) initial baseline assessment done in-person, (2) questionnaires administered by telephone or online via a REDCap weblink during the course of 6 weeks, (3) post-intervention questionnaires administered by telephone or online via a REDCap weblink 4 weeks post-intervention and (4) the patient's medical record. The patient's medical records will be reviewed by the RA at the beginning of the study to collect demographic data and at the conclusion of the study to collect post-intervention data. Private identifiable information will be collected and data will be linked to living individuals. Only members of the research team will have access to the materials.

While there is a small risk of breach of confidentiality, we will take steps to minimize the risk for participants in Aims 2 and 3. The I-HoME software will be provided by Doxy.me, which provides a secure HIPAA compliant platform to conduct synchronous video visits. Data collected for Aim 2 and 3 will be stored on the REDCap database. Precautions will be taken to protect the security of the data collected and the privacy of the individuals from whom we collected the data. All protected identifiers will not be recorded on the same instrument where record data will be obtained from study subjects. Demographic and survey data collected at the subject's home will be entered into REDCap while on-site in order to eliminate the risk of stolen or lost data during transportation. For interviews being conducted at the subject's home, an encrypted audio recorder will be used to reduce risk of data being accessed if stolen.

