#### Safety Alerts

- Severe medical problem of caregiver
- Patient and/or caregiver abuse
- Patient and/or caregiver threatens to harm him or herself or others

A summary of all serious adverse events and safety alerts (i.e., those that are anticipated and related to the study) will be reported to the NIA Program Officer and Safety Officer quarterly, unless otherwise requested by a Safety Officer.

When serious adverse events occur that are unanticipated (i.e., events that are not listed above) and are related to the study (i.e., there is a reasonable possibility that the incident, experience, or outcome may have been caused by the procedures involved in the research), they will be reported to the NIA Program Officer within 48 hours of the study's knowledge. Unanticipated problems involving risks to study participants or others will also be reported to NIA within 48 hours. Unanticipated problems are defined as any incident, experience, or outcome that is unexpected given the research procedures that are described in the protocol-related documents; related or possibly related to participation in the research; or suggest that the research places participants at a greater risk of harm than was previously known or recognized.

[name], the PI, will be responsible for ensuring participants' safety on a daily basis. He will also evaluate the progress of the study, review procedures for maintaining the confidentiality of data, the quality of data collection, management, and analyses.

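### No patient medical event is on the list that triggers a safety report, so patient medical harm is not systematically recorded or reviewed by arm during the trial

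*Combined protocol and SAP*

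**What the plan says.** Section A.1 names two categories of adverse event and then lists the specific events that call for a formal response.

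- Serious adverse events: "Hospitalization of caregiver", "Institutionalization of caregiver", "Emergency room visit of caregiver" and "Death of caregiver".
- Safety alerts: a severe medical problem of the caregiver, "Patient and/or caregiver abuse", and a threat by patient or caregiver to harm themselves or others.

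Events are found through self-report and staff contact. They go on the Alert/Adverse Event Form in REDCap and to the principal investigator within 24 hours (A.2). The monitoring report (C.1) names adverse events and safety events but no patient outcome.

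The Aim 1 section describes symptom care for the patient through "standardized assessments and management that incorporate education, non-pharmacologic and pharmacological therapies". The Aim 3 section says this comes on top of standard hospice care. Patient charts are reviewed at the start and "at the conclusion of the study to collect post-intervention data" (statement of risks and benefits). Live discharges and hospitalizations appear in the monitoring plan's Specific Aims, but as efficacy outcomes.

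**The concern.** The intervention is aimed partly at the patient's pain, dyspnea, nausea, vomiting and agitation. A direct harm from it could therefore fall on the patient: a medication problem, a symptom handled badly, or an avoidable emergency visit. The trigger list looks at the other member of the pair.

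The safety monitor must weigh participant risk against benefit and recommend at each meeting whether to continue or terminate (Safety Monitor Responsibilities; Meeting Format). No planned table of patient events by arm supports that recommendation. An imbalance in patient admissions or deaths could build up between meetings held every 6 to 9 months, with nothing in the plan that would bring it together for review.

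**Working it through.** The plan gives no figure to reproduce here. The check is a count of the list, a reading of the other reporting routes, and a sense of scale.

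**Count of triggers (A.1).**
- Serious adverse events: 4 caregiver, 0 patient.
- Safety alerts: 1 caregiver only, 2 patient or caregiver (abuse; threats of harm).
- Items that are a patient medical event (death, emergency visit, hospitalization, symptom crisis, drug effect): 0 of 4 + 3 = 7.

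**Other routes.**
- Serious events not on the list go to the NIA Program Officer within 48 hours if study-related. So do unanticipated problems involving participants or others.
- Study-related adverse events go to both IRBs (A.2).
- The quarterly summary covers events that are anticipated and related.
- Each route needs someone to notice a single event and classify it. A.1 gives no definition of serious apart from the caregiver list.
- Table 2 takes discharge reason and use of inpatient and respite care from the patient's chart. It has no emergency-visit item, and nothing sends chart data to the safety monitor.

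**Number of patients.** In pairs receiving I-HoME: 10 (Aim 2) + 50 (Aim 3) + 6 (Aim 4) = 66. Controls: 50.

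**Why case-by-case judgement is weak.** The power section gives patient mortality of 35% at four weeks and 62% at eight.
- Expected deaths per arm of 50: 50 × 0.35 = 17.5 by week 4; 50 × 0.62 = 31 by week 8.
- Suppose, for illustration, that week-4 mortality were 45% in one arm: 50 × 0.45 = 22.5, which is 5 more than 17.5. Each of those deaths would look like an ordinary hospice death. Only a count by arm could show the excess.

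**What a count could show.** Assumptions: two-sided alpha 0.05, comparison of two proportions, 50 per arm, no allowance for clustering by nurse (which would lower power).
- 45% against 35%: power 17%.
- 50% against 35%: power 33%.
- 80% power needs about 63% against 35%, a gap of about 28 points.

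**Comparability of the arms (Aim 3, Measurements).** Control charts are read for 11 weeks from enrolment. Intervention charts are read to 4 weeks after the final visit, or to program end if earlier. With a final visit in week 1 to week 6, that is at most 1 + 4 = 5 to 6 + 4 = 10 weeks. The control window is then 11/10 = 1.1 to 11/5 = 2.2 times as long. Follow-up ends at death in either arm, so the difference matters most where visits stop while the patient is alive. Counts taken over these windows would not be comparable.

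**The case against.** The strongest reply is that the plan has more routes than its list.

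- Two of the three alerts name the patient.
- The plan defines an unanticipated serious event as one not on the list, so an unlisted patient event qualifies at once. It then needs only a reasonable possibility of a link to the study.
- A.1 also describes adverse events broadly, as situations found at any follow-up or contact. Staff might therefore complete the form for a patient event.
- The monitor's first meeting is meant to settle how events are identified and reported, and the Manual of Procedures is not among the documents.

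All of this stands. A reader might infer that patient harm goes entirely unseen, that the monitor receives no patient events, or that the unanticipated-problem clause is the only route left. The documents support none of these.

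A reader might also infer that charts are opened only when the whole trial ends. The windows are set per participant, so the conclusion meant may be each participant's own. Under either reading, the chart data are not routed to the monitor.

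Nor do the documents support reading the limit on symptom scores, "the ESAS data collected will not be shared with the clinical team and is for research purposes only", as a conflict with the distress safeguards. Those safeguards concern distress during surveys and suicidality. The limit concerns the clinical team, not the safety monitor.

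What the reply does not supply is a defined set of patient events collected in the same way in both arms and put before the monitor.

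**Conclusion.** The point holds in a limited form. No patient medical event is among the 7 listed triggers or named in the monitoring report, although the intervention manages patient symptoms with drugs among other means. What is missing is systematic recording and review by arm; individual reporting remains possible. It concerns up to 66 patients in pairs receiving I-HoME and 50 controls.

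Keeping expected deaths out of expedited reporting is reasonable in hospice. It does not justify leaving them out of periodic review. A reader might infer that listing patient events would let the trial detect a harmful difference between arms. With 50 per arm it usually would not: power is 33% for 50% against 35% mortality.

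The conclusion rests on reading the A.1 list as the operative trigger, which its introduction supports, and on the Manual of Procedures not already filling the gap. It affects safety oversight only. No sample-size or power figure in the plan changes.

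**What to change.** 1. **A.1.** For both arms, add to the existing Alert/Adverse Event Form: patient emergency visits, unplanned hospital admissions, and any medication or symptom-management problem possibly linked to a study contact. Record relatedness for each. State that deaths from the terminal illness are expected, and are tabulated rather than expedited.
2. **C.1.** Give the safety monitor patient deaths, hospitalizations, emergency visits, live discharges and possibly related events by arm, in the closed session. Use the charts staff already review, and one window of equal length from enrolment in both arms.
3. **Collection.** Put a short prompt in the weekly survey, which both arms complete on the same schedule, and add emergency visits to the chart items. Aim 4 has no weekly survey, so capture these events at the tele-visits and the exit interview.
4. **Timing.** The Aim 4 rationale refers to data already collected. Aim 3 charts can still be tabulated, and Aim 4 can be covered prospectively.

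**Cost.** An amendment to the monitoring plan and form, more event forms (patient events are frequent in hospice), and an added prompt in existing contacts. Some difference in ascertainment will remain because intervention caregivers have more contacts, so chart-based counts should carry most weight. The change concerns recording and reporting only; it proposes no clinical rule.

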#### Safety Alerts

- Severe medical problem of caregiver
- Patient and/or caregiver abuse
- Patient and/or caregiver threatens to harm him or herself or others

A summary of all serious adverse events and safety alerts (i.e., those that are anticipated and related to the study) will be reported to the NIA Program Officer and Safety Officer quarterly, unless otherwise requested by a Safety Officer.

When serious adverse events occur that are unanticipated (i.e., events that are not listed above) and are related to the study (i.e., there is a reasonable possibility that the incident, experience, or outcome may have been caused by the procedures involved in the research), they will be reported to the NIA Program Officer within 48 hours of the study's knowledge. Unanticipated problems involving risks to study participants or others will also be reported to NIA within 48 hours. Unanticipated problems are defined as any incident, experience, or outcome that is unexpected given the research procedures that are described in the protocol-related documents; related or possibly related to participation in the research; or suggest that the research places participants at a greater risk of harm than was previously known or recognized.

[name], the PI, will be responsible for ensuring participants' safety on a daily basis. He will also evaluate the progress of the study, review procedures for maintaining the confidentiality of data, the quality of data collection, management, and analyses.

### A.2 Frequency of Data and Safety Monitoring

When an alert or adverse event is identified by a member of the research team, the event must be reported to [name] within 24 hours and recorded on the Alert/Adverse Event Form in the study's REDCap database. [name] will report any adverse events related to the study to the Weill Cornell Medicine IRB and the VNSNY IRB, according to IRB policy. When serious adverse events occur that are unanticipated (i.e., not listed in the Data and Safety Monitoring Plan) and that are related to the study, they will be reported to the NIA Program Officer within 48 hours of the study's knowledge of the serious adverse event.

### A.3 Protection Against Study Risks

#### Informed Consent

Screening of potentially eligible participants (hospice patients and caregivers) will be conducted by telephone by a study staff member using an IRB-approved screening template. Study staff will explain the study as well as randomization procedures (if applicable), and answer any questions.

If the dyad (hospice patient and caregiver) agrees to participate after hearing the above description, a scheduled visit will be arranged. During this face to face visit, the hospice patient and caregiver participant will be asked to sign a written informed consent to be part of the study. A copy of the consent will be provided to them as well. Participants enrolled in the study will then undergo a baseline interview and proceed with the study protocol as outlined in the other sections of the grant. Throughout the study period and with each interaction with the study team, each participant will be encouraged to ask questions and told that even if they consent to be in the study, they are free to withdraw from it at any time, for any reason.

The main points that will be addressed by study staff obtaining informed consent include explaining why the current research study is being conducted, the source of funding for the project, and what purpose the proposed research serves. Additionally, the subject will be made aware of who is responsible for conducting the research as well as how participants, including themselves, are selected for participation in the research.

The study staff will explain in explicit detail what will be asked of the participants if they agree to participate in the study and estimate the potential time commitment involved. Participants will know what their responsibilities will entail, what risk or benefit may be involved and what potential costs could be incurred should they agree to participate. The study staff will underscore the importance placed upon maintaining participant confidentiality as well as their rights while involved in the study, which includes the right to withdraw participation at any time during the research due to the fact that their participation is entirely voluntary in nature.

The informed consent will also contain a section dedicated to explaining what constitutes protected health information and how this information remains confidential per HIPAA (Health Insurance Portability and Accountability Act) guidelines.

Finally, the informed consent will provide contact information for both Principal Investigators, the Office for the Protection of Research Subjects, and the Site PI contact. All informed consent processes will adhere to the policies set forth by the Institutional Review Board. All informed consent forms will be stored in a locked file cabinet or locked computer file in a locked office to maintain the privacy of all study participants.

In summary, the consent form will include a description of all study procedures, information regarding the risks and benefits of participation, contact information for study staff who can answer participants' questions, and alternatives to participation in the study. The consent form will also state that: (1) participation is voluntary, (2) participants can refuse to answer any questions, (3) participants can withdraw from the study at any time, (4) all responses will remain confidential, and (5) participation in the study is not related to care received while in hospice.

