There is a minimal risk of subject distress during the administration of surveys (see Appendix B) to patients and CGs during the pilot phase in Aims 2 and 3. As a result, I will have safeguards in place to address subject's distress. All study subjects will be free to refuse to answer any questions or to discontinue study participation at any time. In all cases where there might be concerns for suicidality, referrals to a hotline and mental health services will be provided. In addition, the PHQ-9 will be administered to the subject. If subjects do not answer "not at all" to question 9 in the PHQ-9 survey, the research team member will remain with the participant and call to a trained professional to speak with the participant to create a safety plan which may include a call to 911 if warranted.

For studies that require a DSMB, a **DSMB plan** should be provided in the protocol which should include: number of members, meetings (how often), data that will be reviewed during the meetings and plan regarding dissemination of summary reports (i.e. meeting minutes) to the IRB.

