#### Specific Aims:

**Aim 1:** Employ an iterative user-centered design process to develop I-HoME, a multi-component technology-based care intervention, for home hospice patients and their CGs. Development of I-HoME will incorporate best care practices and evidence-based management along with feedback from key stakeholders, i.e., patients (N=10), CGs (N=10), and hospice providers (N=10), to inform and refine the intervention.

**Aim 2:** Conduct a single armed (N=10 dyads) pilot study with a focus on optimizing data collection protocols and the intervention.

**Aim 3:** Conduct a randomized pilot study to evaluate the feasibility and potential efficacy of I-HoME (N=50) compared to usual care (N=50). Feasibility will be assessed by examining overall accrual, attrition, adherence to the study protocol, and use of the intervention; efficacy will be assessed using patient (symptoms), CG (burden, depression, anxiety, satisfaction with care), and systems (hospice live discharges, hospitalizations) outcomes.

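### The consent form is to promise confidentiality without exception, but the plan's PHQ-9 safety procedure requires staff to involve others after certain answers

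*Combined protocol and SAP*

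**What the plan says.** Section A.3 (Informed Consent) sets out what the consent form will contain. In general terms, "the consent form will include a description of all study procedures, information regarding the risks and benefits of participation". A separate section of the form is to be devoted to "explaining what constitutes protected health information and how this information remains confidential per HIPAA" guidelines. Five specific statements follow, on voluntariness, refusing questions, withdrawal, confidentiality and hospice care. The last two read "4) all responses will remain confidential, and (5) participation in the study is not related to care received while in hospice".

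The Statement of the risks/benefits for the study subjects covers distress during the Aim 2 and Aim 3 surveys. Where there may be concern about suicidality, the PHQ-9 is given. Any answer to its question 9 other than 'not at all' sets off a fixed procedure. Staff stay with the person who gave it, and their next step is described as a "call to a trained professional to speak with the participant to create a safety plan which may include a call to 911 if warranted".

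Section A.1 lists safety alerts among the events that trigger a formal response. They include "Patient and/or caregiver abuse" and threats by the patient or caregiver of harm to self or others. Staff are to pick these up from what participants report and from contact with them.

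**The concern.** Statement (4) covers every response and names no limit. The PHQ-9 procedure singles out one type of response and obliges staff to bring in another person because of it. Both cannot hold for a participant who gives that answer.

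What is at stake is the accuracy of what participants are told when they consent. Someone who discloses suicidal thoughts after an unqualified promise, and is then put in touch with a professional or emergency services, has been misinformed about a foreseeable step. The plan uses oral consent in several places (Aim 2, the Aim 3 patient survey, the exit interviews and Aim 4). There, participants depend all the more on the statements read to them being exact.

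**Working it through.** No arithmetic applies, because the plan gives no figure on this point. The check sets the passages side by side.

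1. **Scope of the promise.** Section A.3, statement (4), covers all responses, without a qualifier. PHQ-9 answers are survey responses, so they fall within it.

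2. **Scope of the escalation rule.** The Statement of the risks/benefits applies the rule to any answer to question 9 other than 'not at all'. The call to a trained professional is mandatory, and nothing makes it depend on the participant's agreement.

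3. **Whether the rule takes a response beyond the promise.** The text does not say whether the trained professional belongs to the research team. It does allow for a call to 911, and emergency services are plainly outside the team. So on at least one branch of the procedure, the concern raised by an answer leaves the study.

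4. **Whether an exception appears elsewhere.** Section A.3 mentions HIPAA and tells staff to stress confidentiality, but names no safety limit. The Statement of the risks/benefits restricts access to the Aim 2 and Aim 3 materials to the research team, which strengthens the absolute reading. No passage supplies the exception.

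5. **The other triggers.** Section A.1 adds disclosed abuse and threats of harm as events requiring a formal response. This supports the point but is weaker evidence. Section A.2 specifies a report to the investigator within 24 hours and an entry in the study database, both within the team. The quarterly report to the funder and Safety Officer is a summary, and section C.3 says the safety monitor will not know participants' identities. The PHQ-9 rule is the firm evidence and is sufficient alone.

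6. **Statement (5).** The Aim 1 section describes I-HoME as "effectively evaluating and treating these symptoms along with other EoL symptoms", and the Specific Aims in the monitoring plan include "systems (hospice live discharges, hospitalizations) outcomes". Against that, the Aim 3 section keeps standard home hospice care in place for the I-HoME group, with I-HoME added to it, and gives controls usual services. Statement (5) comes at the end of a list about voluntary participation. It reads naturally as an assurance that hospice care does not depend on taking part, and on that reading there is no contradiction.

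**The case against.** The strongest objection is that the consent form was not available. Section A.3 is a summary of it, and the same paragraph requires the form to describe all study procedures and risks. The PHQ-9 step is a procedure tied to a stated risk, so the form may well describe it. This stands as a limit on the finding, which concerns the protocol's specification of the form and not the form itself. It does not remove the inconsistency. A form that described the escalation step and also carried statement (4) as written would contradict itself. A form that already qualified the statement would show that section A.3 misdescribes it.

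A reader might go further in several directions that the documents do not support:

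- **That staff hold conflicting instructions and may hesitate.** Section A.3 governs what the form says. The PHQ-9 rule and section A.2 govern what staff do, and both are unconditional. Nothing tells staff to withhold a disclosure.
- **That routine safety reporting breaches the promise.** Reports to the investigator stay in the team, and summaries to the funder need not identify anyone.
- **That an efficacy outcome is compromised.** Table 2 lists depression without naming an instrument, and Appendix B is not in the available text. The documents do not show that the PHQ-9 is the efficacy measure.
- **That statement (5) is false for the I-HoME group.** This takes the sentence literally and sets aside the Aim 3 text that keeps standard care in both groups. Measuring live discharges or hospitalizations does not make the assurance untrue.

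**Conclusion.** The inconsistency is real and narrow. One of the five listed consent statements, (4), is unqualified where the plan's own safety procedure requires a qualification. It is worth correcting because it bears on what participants are told and is easily mended.

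The conclusion assumes that the form and oral scripts follow section A.3, and that participants would take a promise about all responses at face value. If the form already states the limit, what remains is to bring section A.3 into line with it.

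The documents give no rate of positive answers to question 9 and no rate of safety alerts, so no count of affected participants can be derived. The finding does not depend on one. Statement (5) is at most open to clarification. No sample size, power or error rate is affected.

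**What to change.** Reconcile section A.3 with the Statement of the risks/benefits and with the safety alerts in section A.1 by qualifying statement (4). For example: 'Responses are confidential, except where the study's safety procedures require staff to involve others because of a risk of harm.' This wording refers back to the procedures as they stand. It avoids promising an onward disclosure of abuse that the plan does not define. Check the consent form and each oral-consent script and align them. The escalation procedures themselves stay unchanged.

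Optionally, reword statement (5) to say that the decision to take part does not affect usual hospice care.

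The cost is a wording amendment through the IRBs. The downside is that a few participants, once told of the limit, may hold back an answer.
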